Once-daily Dose Dexlansoprazole-Levofloxacin-based Quadruple Therapy for *Helicobacter pylori* Eradication: A Randomized Controlled Study

Introduction

Helicobacter pylori (HP) infection affects 70–90% of the population in developing countries and 25–50% in developed countries and remains a significant cause of morbidity and mortality(1). It is a major cause of gastric diseases such as chronic gastritis, gastroduodenal ulcers, gastric adenocarcinoma, mucosal-associated lymphoid tissue lymphoma (MALT lymphoma) and other extragastric diseases. It is well known that the eradication of HP infection is important in preventing and treating these gastric diseases (2, 3). Therefore, a safe and effective eradication regimen for this infection is imperative (4). Triple therapy (TT) regimens including proton pump inhibitors (PPIs), clarithromycin and amoxicillin has regarded as a first-line HP eradication regimen for a long time. However, eradication rate of TT has declined primarily due to increased bacterial resistance to clarithromycin. From this reason, several regimens have proposed as an alternative to eradicate HP infection (5). Levofloxacin-based quadruple therapy for HP eradication has shown to increase cure rate with minimal side effects and has used as a second line treatment for HP infection. Proton pump inhibitor (PPI) is one of the key drugs in anti-HP regimens. It has anti-*H pylori* activity by increasing bioavailability and activity of some antibiotics by reducing gastric acid secretion (6, 7). All PPIs have been used as twice-daily dosing for HP eradication. Dexlansoprazole is a new-generation proton pump inhibitor and exhibiting high efficacy in the treatment of symptoms and lesions associated with erosive esophagitis caused by gastroesophageal reflux disease (GERD)(8). It has dual release of the active drugs that resulting in two peak concentrations at various times, and has long acid suppression activity up to 24 hour. However, one of the study from Thailand showed the excellent eradication rate of dexlansoprazole-based quadruple therapy (more than 95%) (9). From its long duration of acid suppression activity by its dual delayed release formulation. This study was designed to test whether dexlansoprazole can be used as once-daily for HP eradication.

Materials and Methods

Patients and Study Design

A prospective, randomized, open-label, parallel design clinical trial, was conducted from January 2017 to September 2017 at Ramathibodi hospital, Bangkok, Thailand. Eligible patients aged 18-75 years who were diagnosed as HP positive by one of the following two methods: 1) a positive rapid urease test (CLO test).2) histologic evidence of HP by modified Giemsa staining were enrolled to the study. Exclusion criteria were 1) Patients with previous history of HP eradication therapy; 2) patients who has taken drugs that could influence the study results such as a PPI, H2 blocker, mucosal protective agent, or antibiotics within the prior 4 weeks; 3) patients with previous gastric surgery; 4) patients with active malignancies; 5) patients with decompensated liver cirrhosis; 6) patients who have abnormal renal function or chronic kidney disease; 8) patients with previous history of contraindications or allergic reactions to the study drugs; 9) patients with mental disorders or alcohol or drug addiction; 10) pregnancy or lactation or refusal to use an appropriate method of contraception throughout the course of the study; 11) patients with any conditions that might affect the evaluation of the clinical results in the judgment of the principal investigator or sub-investigator. The study protocol was approved by ethic committee of Faculty of Medicine Ramathibodi hospital, Mahidol university.

[figure not shown]

Fig. 1 Flowchart of participants

The diagnosis of HP infection

During the endoscopy, 4 biopsy samples, 2 from gastric antrum and 2 from gastric body were obtained for rapid urease test and histological examination. The presence of HP was defined as: positive tests (rapid urease test or histology). After obtaining informed consent, each enrolled patient was randomly assigned to receive Once-daily (60 mg od) or Twice-daily (60 mg bid) dose dextansoprazole based on quadruple therapy (levofloxacin 500 mg once daily, amoxycilin 1000 mg twice daily, bismuth subsalicylate 1048 mg twice daily) for 14 days. A ¹³C urea breath test was performed to confirm HP eradication at least 6 weeks after treatment to evaluate the result. All the enrolled patients were tested for HP eradication rate in intention to treat (ITT) analysis. Patients who stopped taking the medication due to severe adverse effects, poor compliance, or loss to follow-up were excluded from the per protocol (PP) analysis.

Therapeutic regimens

Randomization was generated by reference to a computer-generated list. The subjects were randomized in a 1:1 ratio by a block of four randomization method to receive either Once (60 mg) or Twice (120 mg)-daily dose Dexlansoprazole based on quadruple therapy (levofloxacin 500 mg OD, Amoxycilin 1000 mg bid, bismuth subsalicylate 1048 mg bid).

Post-therapy follow-up

At least 6 weeks after completion of therapy, ¹³C-urea breath test (UBT) was test in all patients to assess HP eradication. Successful eradication was defined as a negative result from UBT. Pill count was used and drug consumption over 85% was defined as good compliance. Side effects were assessed by personal interview using open-ended questions. The potential adverse events listed in the questionnaires were diarrhea, taste distortions, nausea, vomiting, abdominal pain, dizziness and skin rashes. New symptoms and exacerbation of pre-existing symptoms during the treatment period were considered to be therapy-related adverse events. Serious adverse events were defined as events that disturbed on daily activities.

Sample size and Statistical analysis

The students's t-test, Pearson's chi-squared test and Fisher's exact test were used to determine the parametric difference and nonparametric proportions between the two study groups. Because the eradication rate of the quadruple therapy was found to be 96.0 % in a previous Thai report (9) the

eradication rate of the Once-daily dose dexlansoprazole based on quadruple therapy was assumed to be similar to that of the Twice-daily dose dexlansoprazole based on quadruple therapy if the rate difference between the two regimens was less than 15 %. All tests of significance were two-tailed with a p value less than 0.05

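### Does an 85% pill-count rule that is not set per drug let a twice-daily patient who took dexlansoprazole once a day stay in the per-protocol set?

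*Protocol*

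**What the plan says.** In the protocol, Post-therapy follow-up sets the compliance rule: "Pill count was used and drug consumption over 85% was defined as good compliance". No drug is named, and neither a pooled nor a per-drug count is specified.

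The PP set is described under The diagnosis of HP infection: "Patients who stopped taking the medication due to severe adverse effects, poor compliance, or loss to follow-up were excluded from the per protocol (PP) analysis". No percentage is attached to poor compliance there. The same section includes all enrolled patients in the ITT analysis.

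That section also fixes the regimens. Patients are "randomly assigned to receive Once-daily (60 mg od) or Twice-daily (60 mg bid) dose dextansoprazole", with companion drugs that are the same in both arms: "levofloxacin 500 mg once daily, amoxycilin 1000 mg twice daily, bismuth subsalicylate 1048 mg twice daily) for 14 days". Dexlansoprazole frequency is therefore the only randomised difference.

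Under Sample size and Statistical analysis, the regimens are taken as similar "if the rate difference between the two regimens was less than 15" percent. The protocol does not say whether that criterion is judged on ITT, on PP or on both.

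**The concern.** One threshold covers a four-drug regimen in which only one drug differs between arms. If the count is pooled, the companion drugs can carry a patient over 85% even when dexlansoprazole was not taken as assigned. On a simple dose count the coincidence is exact: the twice-daily arm may miss 14 doses, and 14 doses is the whole difference between the arms. A patient who in effect received the other arm's regimen could then count as compliant.

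The PP wording adds to the worry. Read literally, it covers patients who stopped medication, not those who under-dosed but carried on, and it does not refer to the 85% rule.

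What would be at stake is the PP comparison. In a trial asking whether two regimens are similar, patients in one arm who take the other arm's treatment pull the difference towards zero and so favour the similarity conclusion. ITT keeps such patients by design, so PP is the analysis that could remove them.

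**Working it through.** The protocol states no figure to reproduce here; the check is a count from its regimens.

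**Inputs.** Duration is 14 days. Daily doses are dexlansoprazole 1 or 2 by arm, levofloxacin 1, amoxicillin 2 and bismuth 2 (The diagnosis of HP infection). The threshold is strictly over 85% (Post-therapy follow-up). Units per dose are not given, so one unit per dose is assumed first and then varied.

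**Twice-daily arm, pooled.**
- Total: 28 + 14 + 28 + 28 = 98 doses.
- 0.85 × 98 = 83.3, so at least 84 must be taken and at most 14 missed.
- Dexlansoprazole once a day, all else in full: (98 − 14)/98 = 84/98 = 85.7%, a pass.
- One further missed dose of any drug: 83/98 = 84.7%, a fail.

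**Twice-daily arm, per drug.** The same patient has 14/28 = 50% for dexlansoprazole, a fail. The rule would need at least 24 of 28 (0.85 × 28 = 23.8).

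**Sensitivity to units per dose.** Each companion drug is given one or two units per dose (8 combinations).

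| Dexlansoprazole units per dose | Range of pooled score | Combinations over 85% |
|---|---|---|
| 1 | 84/98 = 85.7% to 154/168 = 91.7% | 8 of 8 |
| 2 | 98/126 = 77.8% to 168/196 = 85.7% | 1 of 8 |

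So the pass depends on how dexlansoprazole is dispensed, which the protocol does not state.

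**Effect on the PP difference.** Let a share f of twice-daily PP patients take the once-daily regimen and eradicate at its rate. The observed difference is then (1 − f) times the true one. For a true gap of 15 points:
- f = 5%: 0.95 × 15 = 14.25
- f = 10%: 0.90 × 15 = 13.5
- f = 20%: 0.80 × 15 = 12

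The protocol gives no value for f; these are illustrations.

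**Offset in the once-daily arm.** Total: 14 + 14 + 28 + 28 = 84 doses. 0.85 × 84 = 71.4, so at least 72 must be taken and 12 may be missed. A patient missing 12 of the 14 dexlansoprazole doses passes (72/84 = 85.7%); one taking none fails (70/84 = 83.3%). If amoxicillin and bismuth are two units per dose, taking no dexlansoprazole also passes (126/140 = 90.0%). If a share g of once-daily PP patients do this and lose d points of eradication, the PP difference becomes (1 − f) × 15 + g × d. The shrinkage is cancelled when g × d = 15f, for example f = 10%, g = 10%, d = 15: 13.5 + 1.5 = 15. A larger g × d widens the difference beyond its true value.

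**The case for a change.** The best case for a change is that the protocol did not leave these rules to a later document. It states a threshold and a PP exclusion, and the two readings of the threshold give opposite answers for the patient who matters most to the randomised comparison. Two sentences would settle it, with the percentage and the treatment unchanged. Nor does the uncertain direction rescue the rule: on a pooled count, PP membership does not depend on taking the assigned dexlansoprazole regimen in either arm.

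Part of this stands. The text does leave per-drug and pooled counts open, the link between the 85% rule and the PP exclusion is unwritten, and spelling both out would be tidier.

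The rest is weaker. The wording does not call for a pooled count, and a per-drug count removes the problem. The literal reading of the PP sentence is strained: its list includes loss to follow-up, which is not a reason for stopping medication, so it reads more naturally as three separate reasons for exclusion. Poor compliance is then the ordinary reverse of the good compliance the protocol defines, and patients who under-dosed without stopping are covered. That reading does not itself choose between pooled and per-drug counting, but it leaves an analyst with only one scoring choice to make.

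The remedy has limits too. The protocol describes conduct in the past tense and does not say that counts were recorded by drug, so a new definition now might not be computable and would have to be labelled a post hoc sensitivity analysis. Requiring over 85% on each of four drugs would also remove more randomised patients from the PP set.

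**Conclusion.** No change to the plan is needed. The figures are correct: 85.7% pooled against 50% per drug for the patient described. They show that the wording is incomplete, not that anything the protocol states is wrong. The pass requires a pooled count, one unit per dexlansoprazole dose (with two units it survives in 1 of 8 combinations) and, on the dose count, a patient who skips half the dexlansoprazole doses and misses none of the other 70.

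The consequence has no established size or sign. The shift at a 15-point gap is 0.75 points at an assumed 5% frequency and 1.5 points at 10%, and selective non-adherence in the once-daily arm could cancel or reverse it. The ITT analysis is unaffected, and the protocol does not rest the similarity criterion on PP alone.

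What remains is a gap in how a pill count is scored and mapped to the PP set. That is routinely written into a statistical analysis plan, which for this trial may exist but is not at hand, or settled by the analyst. The sensible reading is available from the text as it stands: judge consumption against each drug's assigned count and treat 85% or less as poor compliance.

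### The protocol defines serious adverse events by disturbance of daily activities, a severity criterion, so a count reported as serious could include troublesome but non-serious symptoms

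*Protocol*

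**What the plan says.** The definition stands in one sentence of the protocol, under Post-therapy follow-up: "Serious adverse events were defined as events that disturbed on daily activities". The same section describes how events were collected: "Side effects were assessed by personal interview using open-ended questions". It adds that the potential events on the questionnaires "were diarrhea, taste distortions, nausea, vomiting, abdominal pain, dizziness and skin rashes".

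Neither this section nor any other gives a second criterion for *serious*, and there is no mild, moderate and severe grading. The word *severe* appears once, under The diagnosis of HP infection, in the rule for the per-protocol set: "Patients who stopped taking the medication due to severe adverse effects, poor compliance, or loss to follow-up were excluded". It is not defined there and is not linked to *serious*.

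The Sample size and Statistical analysis section lists tests that "were used to determine the parametric difference and nonparametric proportions between the two study groups". It does not say which endpoints they apply to. The design paragraph describes the study in the past tense: "A prospective, randomized, open-label, parallel design clinical trial, was conducted from January 2017 to September 2017".

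**The concern.** In trial reporting *severe* and *serious* answer different questions. Severity is the intensity of an event, and interference with ordinary activity is a usual way to grade it. Seriousness depends on what the event was or led to: death, threat to life, admission to hospital, lasting or significant disability, and so on. The protocol attaches the label *serious* to the first idea.

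What is at stake is the meaning of a safety figure. The Introduction says that "a safe and effective eradication regimen for this infection is imperative", so a reader would naturally take a count of serious events as a statement about safety. Under the protocol's rule the count could contain bothersome symptoms that carry no serious outcome. It could not then be compared with serious-event counts from trials that define the term by outcome.

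**Working it through.** No arithmetic applies. The protocol gives no serious-event rate, count or threshold, so there is no figure to reproduce. The check is a reading of the whole document for anything that would narrow or override the definition.

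1. **Criterion.** The sentence on serious events has one condition, that the event disturbed daily activities. It says nothing about how much or for how long.
2. **Outcome.** No section names death, threat to life, hospital admission or its prolongation, disability, congenital anomaly or medical importance as a criterion for *serious*. Nothing in the stated rule brings outcome in.
3. **Overlap with a true seriousness criterion.** Significant incapacity is an accepted ground for calling an event serious, and it does concern daily functioning. It implies a substantial degree or persistence, however. The protocol's wording has no such threshold and is therefore much broader.
4. **Events to which the rule applies.** The listed events are diarrhea, taste distortion, nausea, vomiting, abdominal pain, dizziness and skin rash. Each can upset a patient's day without any serious outcome. Taking dizziness as an example: it occurs during treatment, the patient gives up normal activities for a day, and it resolves. The stated condition is met and the event is labelled serious, though no outcome criterion is met.
5. **Other uses of related terms.** The per-protocol rule speaks of severe adverse effects. The two words may have been interchanged in drafting. If so, the criterion was meant as one of severity and the label is wrong. If not, the label was meant and the criterion is wrong. The sentence needs correcting on either reading.
6. **Size.** The over-count is the number of events that disturbed the day but were not serious by outcome. The protocol gives neither that number nor the number of events serious by outcome. No estimate or useful range follows from it. If no such events occurred, the over-count is zero.

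**The case against.** The strongest case on the other side is about weight. No section makes serious events an endpoint, a stopping criterion or the basis of a conclusion. The stated aim is whether dexlansoprazole can be given once daily for eradication, and the remark in the Introduction about a safe regimen is background on regimens in general. The definition is also open to view, so anyone who reads it knows what would be counted. The English is loose throughout, and a slip between *serious* and *severe* is plausible. All of this stands, and it makes the point minor. It does not remove it: a term with an established safety meaning keeps that meaning when it appears in a results table without its definition. Nor is this a detail left to an analysis plan that is not shown here, because the protocol itself states the rule.

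Three stronger readings are tempting, and the protocol does not support them.

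- A reader might infer that a comparison of serious events between arms is biased, since the trial is open-label. The statistical section names no endpoint for its between-group tests, so testing serious events by arm is not stated, and nothing shows that the definition works differently in the two arms.
- A reader might infer that the per-protocol set is affected. That rule uses a different term and concerns patients who stopped medication. The protocol does not connect it to the definition of *serious*.
- A reader might join the definition to the attribution rule, "New symptoms and exacerbation of pre-existing symptoms during the treatment period were considered to be therapy-related adverse events", and conclude that the protocol inflates serious drug-related harm. Attribution is a separate matter and has no bearing on whether *serious* is the right label.

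It would also go too far to say that the interview could capture symptoms only. Open-ended questions might have brought out admissions or other outcomes. The protocol does not say whether outcomes were recorded, and that limits the remedy.

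**Conclusion.** The point holds as a minor correction to safety reporting. The protocol labels as serious any event that disturbed daily activities, with no threshold and no outcome criterion, so a count under that label could include non-serious symptoms. The conclusion rests on the wording of the definition and on the ordinary distinction between severity and seriousness. It needs no outside figure.

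The size of any over-count is unknown. How far it matters in practice depends on whether a count of serious events is reported under that name, which the protocol does not state. The eradication endpoint, the intention-to-treat and per-protocol analyses and the 15% criterion for the rate difference do not depend on this definition.

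**What to change.** In Post-therapy follow-up, relabel the present criterion *severe adverse event*. If the term *serious* is kept, define it separately by outcome: death, life-threatening event, hospital admission or its prolongation, persistent or significant disability, congenital anomaly, or another medically important event. Report the two categories separately by arm.

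Because the study is described as already conducted, classify an event by outcome only where an outcome was recorded. As the trial was open-label, this should be done without knowledge of treatment arm. Mark the remaining events *not classifiable*, not non-serious. The per-protocol exclusion stays as written, and the relabelled term should not be read back into it.

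The cost is one changed term, one added definition if *serious* is kept, one pass over the recorded events by someone unaware of the arm, and two reported categories in place of one. No new data are needed. The downside is that fewer events can be called serious and some may be unclassifiable. If few outcomes were recorded, relabelling will be most of the benefit.

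### The 15-point rule for calling once-daily dosing similar uses the rate difference with no confidence limit, so a regimen truly 15 points worse passes about half the time

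*Protocol*

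**What the plan says.** The Introduction states the aim: "This study was designed to test whether dexlansoprazole can be used as once-daily for HP eradication". Sample size and Statistical analysis takes a reference rate from an earlier study ("eradication rate of the quadruple therapy was found to be 96.0 % in a previous Thai report") and then says that the once-daily rate "was assumed to be similar to that of the Twice-daily dose dexlansoprazole based on quadruple therapy". The condition attached to this is a threshold on the difference alone: "if the rate difference between the two regimens was less than 15" percent.

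For inference, the same section lists Student's t-test, Pearson's chi-squared test and Fisher's exact test, which "were used to determine the parametric difference and nonparametric proportions between the two study groups", and adds "All tests of significance were two-tailed with a p value less than 0.05". It gives no confidence interval, no non-inferiority hypothesis and no test against a margin. Despite its heading, it gives no sample size or power. Allocation is 1:1 (Therapeutic regimens), and the endpoint is binary: a negative urea breath test at least six weeks after therapy (Post-therapy follow-up).

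**The concern.** A trial meant to justify the less frequent schedule has to rule out an unacceptable loss of eradication. That takes a confidence limit, or an equivalent test, set against the margin. Here the 15 points are compared with the rate difference itself, so sampling error plays no part in the decision.

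The named tests do not fill the gap. Their null hypothesis is equality, and failing to reject equality is not evidence of similarity, least of all in a small trial.

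At stake is the main conclusion. Once-daily dosing could be reported as similar while the data remain compatible with a loss well beyond the protocol's own 15 points.

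**Working it through.** **Inputs.** From the protocol: twice-daily rate 96%; threshold 15%, read as percentage points; 1:1 allocation; two-sided 0.05. Assumed: patients per arm *n*, because none is stated; a range is shown. The protocol gives no sample size or power, so there is no figure of its own to reproduce.

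**Step 1. The rule at the margin.** Let *D* be the observed twice-daily minus once-daily rate. If the true difference is exactly 0.15, then approximately P(*D* < 0.15) = Φ((0.15 − 0.15)/SE) = Φ(0) = 0.50. The standard error drops out, so *n* does not matter. Exact enumeration of two independent binomials agrees; the scatter around one half comes from discreteness.

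| n per arm | called similar, 96% vs 81% | called similar, 96% vs 76% |
|---|---|---|
| 27 | 59% | 36% |
| 36 | 52% | – |
| 50 | 51% | 23% |
| 100 | 46% | 12% |

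For *n* from 20 to 200 the 96% vs 81% figure lies between 41% and 59%. With control rates of 85%, 90% or 99% and a true 15-point loss it is 46–54% for *n* = 30 to 100.

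**Step 2. Beyond the margin.** For a true 20-point loss at *n* = 50, SE = √[(0.96×0.04 + 0.76×0.24)/50] = √(0.2208/50) = 0.066, and Φ((0.15 − 0.20)/0.066) ≈ 0.23, as in the table. Here a smaller trial is more likely to pass, so the rule rewards imprecision.

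**Step 3. Do the named tests protect?** Power against 96% vs 81%, two-sided 0.05:

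| n per arm | Fisher | Pearson, uncorrected |
|---|---|---|
| 27 | 19% | 44% |
| 50 | 54% | 70% |
| 100 | 91% | 94% |

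Suppose similarity required both a difference under 15 points and a non-significant Pearson test, which the protocol does not say. A regimen truly 15 points worse would still pass 47% (*n* = 30), 30% (50), 14% (75) or 6% (100) of the time.

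**Step 4. Two possible results.**

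- 48/50 vs 41/50: difference 0.96 − 0.82 = 14 points, so similar by the rule. SE = √[(0.96×0.04 + 0.82×0.18)/50] = 0.061, and the simple upper limit is 0.14 + 1.96×0.061 = 0.26. The Miettinen-Nurminen score limit is 27.5 points. Fisher gives p = 0.051 and uncorrected Pearson p = 0.025, so the two named tests disagree.
- 96/100 vs 85/100: difference 11 points, so similar by the rule, yet Fisher p = 0.014. The score upper limit is 19.8 points, beyond the margin.

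**Step 5. A confidence-limit rule.** Require the upper 95% limit of twice-daily minus once-daily to be below 15 points. At 96% vs 81%, the Miettinen-Nurminen rule passes 1.6–2.3% of the time (*n* = 27 to 100) and the Newcombe rule 1.9–2.6% (*n* = 20 to 200). A simple Wald limit is looser: 3–5% for *n* of 25 or more, and 8.5% at *n* = 20.

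The usual normal approximation with both rates at 96% and one-sided 0.025 gives *n* = (1.96 + 0.84)² × 2 × 0.96 × 0.04 / 0.15² ≈ 27 per arm for 80% power, and 36 for 90% (1.28 in place of 0.84). It is optimistic at so high a rate: exact power of the score rule is 46% (*n* = 27), 70% (36), 87% (50) and above 99% (100).

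**The case against.** The strongest reply is that the protocol never says the *observed* difference. The sentence sits under a sample-size heading, opens with a reference rate and uses the word assumed, so 15% may be a loosely worded planning margin, with the interval method left to an analysis plan that is not shown. That reading is possible. It does not rescue the text: even as a margin, the 15% is used by no stated procedure, because every test named has equality as its null. The sentence needs the same repair on either reading.

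Several narrower points do stand:

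- The one-half figure is the value exactly at the margin. For larger deficits the false pass rate falls as *n* grows.
- Non-significance despite a 15-point loss is common only in smaller trials. At 100 per arm, power is above 90% with either test.
- A significant difference inside a margin is not a contradiction in itself; it can occur under a sound non-inferiority rule too. In the 96/100 vs 85/100 example the trouble is that the upper limit exceeds 15 points.
- The protocol does not make p > 0.05 a condition for similarity. That it would be reported as support is a risk, not a stated rule.
- The protocol describes the trial as conducted from January to September 2017, so a change of criterion now may come after the data.

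None of these touches the missing confidence limit.

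**Conclusion.** The concern holds and must be fixed, because this is the only criterion for the trial's main conclusion. As written, a once-daily regimen truly 15 points worse is called similar about half the time (41–59% over 20 to 200 per arm), against 2.5% for a conventional non-inferiority rule.

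The result rests on reading the 15% as percentage points applied to the rate difference, which is the plain reading. It does not depend on the unstated sample size, and hardly on the control rate. The figures for a 20-point loss and for test power do depend on the assumed arm size.

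**What to change.** Replace the similarity sentence with: *Once-daily dosing is non-inferior if the upper limit of the two-sided 95% score confidence interval (Miettinen-Nurminen or Farrington-Manning) for the difference in eradication rate, twice-daily minus once-daily, is below 15 percentage points in both the ITT and the PP sets.* Both sets are already described under The diagnosis of HP infection. Report chi-squared and Fisher p values as descriptive, and draw no conclusion of similarity from the point estimate.

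A score interval is advised because a failure rate near 4% leaves only a handful of events per arm, where the Wald limit is too lenient. Requiring both sets is a cautious choice, not something the protocol obliges. State the one-sided alpha of 0.025, the power and the number per arm beside the criterion, with power computed exactly.

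The change costs one sentence and one interval from data already collected. The real price is that the trial may fail to show non-inferiority where the present rule would have claimed similarity: with equal 96% rates, power is 46% at 27 per arm and 87% at 50. If outcomes have already been seen, the report should say that the criterion was revised afterwards and show the interval in full.
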